#### 9.4 Exposure to Study Intervention During Pregnancy

Details of all pregnancies in female participants and female partners of male participants will be collected after the start of study intervention and until the Follow-up Visit (Visit 8) or 30 days after the last dose of study intervention if the Follow-up Visit is not done. Study center personnel must report every pregnancy on the pregnancy form within 24 hours of learning of the pregnancy to the **SAE/pregnancy fax number**, [REDACTED] even if no AE has occurred. The pregnancy must be followed to term and the outcome reported by completing a follow-up pregnancy form. Abnormal pregnancy outcomes (eg, spontaneous abortion, fetal death, stillbirth, congenital anomalies, ectopic pregnancy) are considered SAEs. Elective abortions can be SAEs or AEs depending on the reason for the elective abortion (eg, fetal death, still birth, congenital anomalies, ectopic pregnancy, which would make the elective abortion an SAE). For pregnancy-related SAEs, in addition to the pregnancy form, a separate SAE form must be filed as described in Section 9.3 with the appropriate serious criterion (eg, hospitalization) indicated.

#### 9.5 ALT or AST Elevations

A treatment-emergent  $ALT \geq 3 \times ULN$  and/or  $AST \geq 3 \times ULN$  is considered an AE of special interest. Any participant with this laboratory result after study intervention was taken must have repeat testing within 48 to 72 hours to confirm the abnormality. For this repeat testing, the following laboratory tests must be drawn: hematology and chemistry panels, INR, serum acetaminophen level, urine drugs of abuse screen, and blood alcohol level. An extra blood serology sample must be collected and sent to the central laboratory for further diagnostic testing at a later date if needed. In addition, the investigator will perform a complete history and examination to evaluate the participant for possible liver disease.

All AEs of special interest must be reported to Allergan within 24 hours of the time the investigator becomes aware of the event using the abnormal liver function reporting form and the AE eCRF. All new elements of history, physical examination, diagnostic testing results, and other relevant medical reports are to be reported for each AE of special interest.

**If an ALT or AST  $\geq 3 \times$  ULN is confirmed, close medical follow-up is required:** For these participants, the following laboratory tests must be performed: anti-hepatitis A IgM, hepatitis B surface antigen, anti-hepatitis B core IgM, hepatitis C antibody, hepatitis C quantitative RNA by polymerase chain reaction, anti-hepatitis E IgM, anti-hepatitis E IgG, Cytomegalovirus IgM antibody and Epstein-Barr Virus IgM antibody. The participant must be followed clinically and further medical evaluation (for other causes of acute hepatic injury) should be done per the judgment of the investigator and in conjunction with medical personnel at Allergan. In general, the chemistry panel should be repeated 1 to 2 times per week to follow the course of ALT/AST elevation.

**Study intervention must be discontinued if any of the following criteria are met:**

- ALT or AST  $\geq 3 \times$  ULN and the participant is symptomatic with the appearance of fatigue, nausea, vomiting, right upper quadrant pain or tenderness, fever, rash, or eosinophilia ( $> 5\%$ )
- ALT or AST  $\geq 3 \times$  ULN and total bilirubin  $> 2 \times$  ULN
- ALT or AST  $\geq 3 \times$  ULN and INR  $> 1.5$
- ALT or AST  $\geq 5 \times$  ULN for more than 2 weeks
- ALT or AST  $\geq 8 \times$  ULN

The participant may be rechallenged with study intervention only after consultation with the Allergan Medical Monitor. For participants who are not rechallenged with study intervention, they should be discontinued from the study and complete an ET visit (Visit 7/ET assessments) and 4-week Follow-up Visit. Participants should receive appropriate follow-up as per standard of care.

**The investigator must contact the Allergan Medical Monitor to discuss all cases of confirmed ALT/AST elevation  $\geq 3 \times$  ULN. All ALT/AST elevations must be followed until ALT and AST return to  $< 1.5 \times$  ULN and there is full clinical resolution.**

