### 6.5.2 Adverse Events of Special Interest

Selected nonserious and serious adverse events are of special interest and will require immediate reporting, recording, and follow-up. The following events will be closely monitored:

- Treatment-emergent suicidal ideations with intent, with or without a plan, (ie, Type 4 or 5 on the C-SSRS) or any suicidal behaviors.
- Treatment-emergent elevated ALT or AST lab value  $\geq 3 \times \text{ULN}$ .
- Potential Hy's law cases: elevated ALT or AST lab value that is  $\geq 3 \times \text{ULN}$  and an elevated total bilirubin lab value that is  $\geq 2 \times \text{ULN}$  and, at the same time, an alkaline phosphatase lab value that is  $< 2 \times \text{ULN}$ .

Reporting requirements for ALT or AST elevations and potential Hy's law cases are outlined in Section 9.5 and Section 9.5.1. Responses to the C-SSRS that meet the above criterion will be captured in the eTablet and monitored by Allergan. These AEs or events determined to be SAEs must be reported appropriately via the designated eCRFs and safety forms.

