## 8.9 Withdrawal Criteria

Women who become pregnant (Section 9.4) and participants who meet study intervention discontinuation criteria related to abnormal liver function tests (Section 9.5) and advised not to be rechallenged will be withdrawn from the study and should refrain from taking study

intervention. The participant should return to the clinic for early termination procedures (Visit 7) and the Follow-up Visit 8. Participants who reply with “yes” to questions 4 or 5 in the suicidal ideation section or “yes” to any question in the suicidal behavior section of the C-SSRS at Visits 3 through 6 must be withdrawn from the study and should receive appropriate follow-up as in routine clinical practice, including the Early Termination Visit 7 and the Follow-up Visit 8. These participants must continue to complete their daily eDiary through Visit 8 Follow-up.

A participant with a condition and/or a situation that, in the investigator's opinion, may put the participant at significant risk, may confound the study results, or may interfere significantly with the participant's participation in the study must be withdrawn from treatment.

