### 9.5.1 Potential Hy's Law Cases

Sites must report every participant who meets the following potential Hy's law criteria if this occurs within the time the participant signs the ICF until 30 days after the last dose of study intervention:

- ALT or AST  $\geq 3$  x ULN **AND**
- Total bilirubin  $\geq 2$  x ULN **AND**
- Alkaline phosphatase  $< 2$  x ULN

Study site personnel must report every participant who meets these criteria. Typically, all 3 analytes will be obtained from the same sample, but they may come from multiple samples taken within a 24-hour period. This requirement applies from the time the participant signs the ICF for the study until 30 days after the final protocol-defined study visit or the last known dose of study intervention (if the final visit does not occur).

A laboratory alert for possible Hy's law cases will be in place, and must notify investigators and Allergan immediately when the above criteria have been met. A possible Hy's law case must be faxed to Allergan on an abnormal liver function reporting form as soon as possible (within 24 hours of learning of the possible Hy's law case) to the fax number on the form or the SAE fax number, even if no AE has occurred. If the event is serious, please complete the SAE form. The eCRF for possible Hy's law cases must be completed within 7 calendar days. Every effort to determine the cause of the liver enzyme abnormalities must be made, and close monitoring should be initiated in conjunction with the medical monitor and medical safety physician and in accordance with the FDA Guidance for Industry, Drug-Induced Liver Injury: Premarketing Clinical Evaluation, July 2009. The participant should return to the study site and be evaluated as soon as possible, preferably within 48 hours from the time the investigator becomes aware of the abnormal results. This evaluation should include laboratory tests, detailed history, and physical assessment.

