In addition, a tabular display showing all AEs that occurred in participants who had PCS postbaseline clinical laboratory values will be provided.

Shift tables from baseline to end of the double-blind treatment period for clinical laboratory parameters will be presented by treatment group for the following categories: low, normal, and high, which are provided by the laboratory vendor.

Potential Hy's Law criteria within a 24-hour window is defined by a post baseline elevation of alanine aminotransferase (ALT) or aspartate aminotransferase (AST) ≥ 3 x ULN, along with total bilirubin (TBL) ≥ 2 x ULN and a non-elevated alkaline phosphatase (ALP) < 2 x ULN, all based on blood draws collected within a 24-hour period. Potential Hy's Law criteria without time window is defined by maximum of post baseline elevation of ALT or AST ≥ 3 x ULN, along with maximum of post baseline elevation of TBL ≥ 2 x ULN. Patients who meet the potential Hy's Law criteria from the first dose of study drug to the end of study will be summarized. Supportive tabular displays will also be provided.

Table 11–1 Criteria for Potentially Clinically Significant Laboratory Values

			PCS (Criteria
Category	Parameter	SI Unit	PCS Low	PCS High
Chemistry	Albumin	g/L	< 0.8 × LLN	> 1.2 × ULN
	Alanine aminotransferase	U/L		\geq 3.0 × ULN
	Alkaline phosphatase	U/L	_	\geq 3.0 × ULN
	Aspartate aminotransferase	U/L	_	\geq 3.0 × ULN
	Bicarbonate	mmol/L	< 0.9 × LLN	> 1.1 × ULN
	Bilirubin, total	μmol/L	_	$\geq 1.5 \times ULN$
	Blood urea nitrogen	mmol/L		> 1.5 × ULN
	Calcium	mmol/L	< 0.9 × LLN	> 1.1 × ULN

SAP 3101-301-002 AGN-241689

Table 11–1 Criteria for Potentially Clinically Significant Laboratory Values

			Criteria
Parameter	SI Unit	PCS Low	PCS High
Chloride	mmol/L	$< 0.9 \times LLN$	> 1.1 × ULN
Cholesterol, total	mmol/L		> 1.6 × ULN
Creatinine	μmol/L		> 1.5 × ULN
Creatine kinase	U/L		> 2.0 × ULN
Estimated glomerular filtration rate	$mL/min/1.73m^2$	< 60	_
Glucose, nonfasting	mmol/L	$< 0.8 \times LLN$	> 2.0 × ULN
Lactate dehydrogenase (LDH)	U/L		> 3.0 × ULN
Phosphorus	mmol/L	$< 0.9 \times LLN$	> 1.1 × ULN
Potassium	mmol/L	$< 0.9 \times LLN$	> 1.1 × ULN
Protein, total	g/L	$< 0.9 \times LLN$	> 1.1 × ULN
Sodium	mmol/L	$< 0.9 \times LLN$	> 1.1 × ULN
Triglycerides	mmol/L		> 2.0 × ULN
	μmol/L		> 1.2 × ULN
Basophils, absolute cell count			> 2.0 × ULN
Eosinophils, absolute cell count			> 2.0 × ULN
Hematocrit	Ratio	$< 0.9 \times LLN$	> 1.1 × ULN
Hemoglobin	g/L	$< 0.9 \times LLN$	> 1.1 × ULN

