	\geq 20 × ULN
	$\geq 1 \times \text{ULN}$
	≥ 1.5 × ULN
	$\geq 2 \times ULN$
AST	\geq 3 × ULN
	≥ 5 × ULN
	≥ 10 × ULN
	≥ 20 × ULN
	≥ 1 × ULN
	≥ 1.5 × ULN
	\geq 2 × ULN
ALT or AST	≥ 3 × ULN
	≥ 5 × ULN
	≥ 10 × ULN
	\geq 20 × ULN
	$\geq 1 \times \text{ULN}$
	≥ 1.5 × ULN
	$\geq 2 \times \text{ULN}$
Bilirubin Total	\geq 3 × ULN
	\geq 5 × ULN
	$\geq 10 \times \text{ULN}$
	$\geq 20 \times \text{ULN}$
	$\geq 1 \times \text{ULN}$
	≥ 1.5 × ULN
	\geq 2 × ULN
Alkaline Phosphatase	\geq 3 × ULN
	≥ 5 × ULN
	≥ 10 × ULN
	≥ 20 × ULN
Concurrent Elevations ¹	ALT or AST \geq 3 × ULN and Bilirubin Total \geq 1.5 × ULN
	ALT or AST $>= 3 \times ULN$ and Bilirubin Total $\geq 2 \times ULN$
Potential Hy's Law ¹	ALT or AST \geq 3 × ULN and Bilirubin Total \geq 2 × ULN and ALP $<$ 2 × ULN
	•

ALT = alanine aminotransferase; AST = aspartate aminotransferase; TBL = total bilirubin; ALP = alkaline phosphatase; ULN = upper limit of normal (value provided by the laboratory).

¹ Elevations are from the same day

[figure not shown]
The number and percentage of participants with an adjudicated case (i.e., $ALT \ge 3 \times ULN$) and/or $AST \ge 3 \times ULN$) will be summarized by treatment group and by relationship of ALT or AST elevation to study medication. The percentages will be calculated relative to the number of participants with at least 1 adjudicated case. The numerator will be the number of participants with at least 1 adjudicated case in the specific category of relationship. If a participant has more than 1 adjudicated case, he or she will be counted in the most relevant category of relationship.

Participants with an adjudicated case (i.e. $ALT \ge 3 \times ULN$ or $AST \ge 3 \times ULN$) will be listed with their ALT and AST assessments, adjudication dates, relationship of ALT or AST elevation to study medication, and confounding factor(s). Additional listings will be provided for participants who meet $ALT \ge 3 \times ULN$ or $AST \ge 3 \times ULN$ and/or potential Hy's law and have one of the following categories: at least 1 abnormal liver biochemistry risk factor, at least 1 liver disease sign and symptom, at least 1 liver diagnostic test performed, consultation with a specialist for liver evaluation, liver lab tests performed, and drug screen performed, respectively. A listing of urine pregnancy test results will be provided for female participants of child-bearing potential with at least one positive result.

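### The liver stopping rule in Protocol 9.5 just misses a potential Hy's law case with total bilirubin at exactly 2 × ULN; writing ≥ in place of > would close the gap

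*Protocol*

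**What the plan says.** **Stopping.** The discontinuation list in Protocol 9.5 has five criteria, any one of which makes stopping compulsory. The bilirubin criterion combines ALT or AST ≥ 3 × ULN with the condition "and total bilirubin $> 2 \times$ ULN". The other four are:

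- ALT or AST ≥ 3 × ULN with a listed symptom or eosinophilia above 5%
- ALT or AST ≥ 3 × ULN with INR above 1.5
- ALT or AST ≥ 5 × ULN lasting more than 2 weeks
- ALT or AST ≥ 8 × ULN

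**Reporting.** Protocol 9.5.1 defines a potential Hy's law case by ALT or AST ≥ 3 × ULN, "Total bilirubin $\geq 2$ x ULN" and alkaline phosphatase below 2 × ULN. Protocol 6.5.2 uses the same inclusive bilirubin limit. SAP 11.2 does too ("along with total bilirubin (TBL) ≥ 2 x ULN and a non-elevated alkaline phosphatase (ALP) < 2 x ULN"), and so does SAP Table 11-2. Section 9.5.1 calls for a laboratory alert, a report within 24 hours, a search for the cause, close monitoring and prompt evaluation. It does not say that drug must stop.

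**Withdrawal.** Protocol 8.9 links liver-related withdrawal to 9.5, referring to "participants who meet study intervention discontinuation criteria related to abnormal liver function tests (Section 9.5") who are advised not to be rechallenged. It separately requires withdrawal from treatment when, in the investigator's opinion, a condition "may put the participant at significant risk".

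**The concern.** The protocol treats a potential Hy's law case as one of its most serious liver signals. One would expect every such case in a participant still on drug to fall under the compulsory stopping rule. Because 9.5 uses a strict sign and the Hy's law definition an inclusive one, the two rules part at a single value. A participant can set off the immediate alert and still meet no stopping criterion.

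What is at stake is the safety of an individual participant, not inference. At that value, stopping rests on the judgment of the investigator and the Medical Monitor. Liver injury is also the concern the protocol itself raises for this class: section 1.2 reports ALT increases with telcagepant, and section 3.2 sets up a committee to adjudicate ALT or AST elevations of 3 × ULN or more. The documents give no reason for leaving the boundary case outside the rule.

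**Working it through.** The plan gives no figure to reproduce here. The check is one of logic, plus a date calculation to see how far a change could reach.

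**1. The two bilirubin limits side by side (both with ALT or AST ≥ 3 × ULN)**

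| Place | Purpose | Total bilirubin |
|---|---|---|
| Protocol 9.5 | compulsory stop | > 2 × ULN |
| Protocol 6.5.2 | adverse event of special interest | ≥ 2 × ULN |
| Protocol 9.5.1 | potential Hy's law reporting | ≥ 2 × ULN |
| SAP 11.2 and Table 11-2 | potential Hy's law summary | ≥ 2 × ULN |

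Above 2 × ULN, every potential Hy's law case is stopped by the bilirubin criterion. Below 2 × ULN there is no potential Hy's law case. Only equality can separate the rules.

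**2. What happens at equality.** Take bilirubin = 2 × ULN, ALT or AST ≥ 3 × ULN and alkaline phosphatase < 2 × ULN. The bilirubin criterion in 9.5 is not met. Each of the other four criteria may be met or not, which gives 2⁴ = 16 logical patterns.

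- With >: 15 patterns stop and 1 does not.
- With ≥: all 16 stop.

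The remaining pattern has no listed symptom or eosinophilia above 5%, INR ≤ 1.5, ALT and AST below 8 × ULN, and neither at ≥ 5 × ULN for more than 2 weeks. These are logical patterns, not prevalences.

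**3. Confirmation on a grid.** The five stopping criteria and three Hy's law conditions were coded as rules. They were evaluated for ALT/AST from 1.0 to 10.0 × ULN and bilirubin from 0.5 to 4.0 × ULN, both in steps of 0.1, with alkaline phosphatase, INR, symptoms and duration also varied.

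- With >: 50 ALT/AST-by-bilirubin combinations can be potential Hy's law without a stop. All have bilirubin 2.0 × ULN, with ALT/AST from 3.0 to 7.9 × ULN.
- With ≥: none remain.

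**4. Can the value occur?** The documents give neither the bilirubin ULN nor the reporting step. As an assumed example only, with a ULN of 1.2 mg/dL and results in steps of 0.1, a result of 2.4 mg/dL is exactly 2 × 1.2. So the value is attainable, but its frequency cannot be estimated.

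**5. Reach in this trial.** SAP 4 and 18.1 put the last participant's first visit on 31 January 2020, and SAP 4 dates protocol amendment 3 to 14 May 2020. The SAP does not say which visit is meant, so both readings are shown. Protocol 8.4.1 places Visit 1 at Day −35 to Day −28, and Day 84 is 83 days after Day 1.

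| Reading | Day 1 | Day 84 | Relative to 14 May 2020 |
|---|---|---|---|
| Visit 1, at Day −28 | 31 Jan + 28 days = 28 Feb | 21 May | 7 days after |
| Visit 1, at Day −35 | 31 Jan + 35 days = 6 Mar | 28 May | 14 days after |
| First dose | 31 Jan | 23 Apr | before |

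Scheduled dosing had therefore either ended before amendment 3 or had at most about two weeks left.

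**The case against.** The strongest reply is that this is a drafting preference. A reporting trigger can sensibly be inclusive while a stopping rule is strict, and no document requires the two to match. The co-condition cut-offs in the 9.5 list are consistently strict: eosinophilia, bilirubin and INR all use a greater-than sign. That stands, and it is why this is not called an error. Still, both rules chose 2 × ULN and differ only in the sign. Of the three strict cut-offs, only bilirubin has an inclusive counterpart elsewhere for the same signal.

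A second reply is that the boundary case is well guarded. Any ALT or AST ≥ 3 × ULN on treatment "must have repeat testing within 48 to 72 hours to confirm the abnormality". Confirmed cases must be discussed with the Medical Monitor and generally have chemistry repeated once or twice a week, so a participant who worsens should soon meet a stopping criterion. There is also the Hy's law alert, the 8.9 withdrawal on the investigator's opinion, DSMB review and blinded adjudication. This also stands, and it makes the gap narrow and probably brief. It also means that the missing stop is specifically one triggered by laboratory values, since 8.9 can still compel withdrawal through judgment. None of these safeguards makes the stop automatic.

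Third, 9.5.1 asks for monitoring in line with an FDA guidance on drug-induced liver injury, which was not available for this review. Its content is left open. The protocol cites it for monitoring and writes no stop of its own into 9.5.1.

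Finally, the practical value in this trial is slight, given the dates above. That is accepted.

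**Conclusion.** The point holds as a small improvement to the design. As written, a potential Hy's law case at exactly 2 × ULN that meets none of the other four criteria in 9.5 is alerted and closely followed, but no laboratory criterion compels stopping. It is the only kind of potential Hy's law case outside the 9.5 rule.

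The practical weight is very small: very few participants, possibly none. The logical conclusion rests only on the wording of the criteria and is firm. How often the value occurs is unknown, and the remaining reach in this trial depends on which visit the SAP means by first visit. No efficacy analysis, power figure or error rate is affected.

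**What to change.** In the bilirubin criterion of Protocol 9.5, replace > 2 × ULN with ≥ 2 × ULN. Protocol 6.5.2 and 9.5.1 and the SAP can stay as they are. Every potential Hy's law case in a participant on study drug would then also be a compulsory stop. The new sign would also stop boundary cases with alkaline phosphatase ≥ 2 × ULN, which fits the existing criterion because it sets no alkaline phosphatase condition.

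The text change is one symbol, with no new data, procedure or analysis. The administrative cost is larger: Protocol 10.3 requires sponsor approval and prior IRB/IEC approval of an amendment, across about 110 sites (Protocol 4.1). The change should therefore travel with another amendment and does not justify one alone. The clinical cost is that a rare boundary participant stops drug. Section 9.5 allows rechallenge after consultation with the Medical Monitor.

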### 9.5.1 Potential Hy's Law Cases

Sites must report every participant who meets the following potential Hy's law criteria if this occurs within the time the participant signs the ICF until 30 days after the last dose of study intervention:

- ALT or AST  $\geq 3$  x ULN **AND**
- Total bilirubin  $\geq 2$  x ULN **AND**
- Alkaline phosphatase  $< 2$  x ULN

Study site personnel must report every participant who meets these criteria. Typically, all 3 analytes will be obtained from the same sample, but they may come from multiple samples taken within a 24-hour period. This requirement applies from the time the participant signs the ICF for the study until 30 days after the final protocol-defined study visit or the last known dose of study intervention (if the final visit does not occur).

A laboratory alert for possible Hy's law cases will be in place, and must notify investigators and Allergan immediately when the above criteria have been met. A possible Hy's law case must be faxed to Allergan on an abnormal liver function reporting form as soon as possible (within 24 hours of learning of the possible Hy's law case) to the fax number on the form or the SAE fax number, even if no AE has occurred. If the event is serious, please complete the SAE form. The eCRF for possible Hy's law cases must be completed within 7 calendar days. Every effort to determine the cause of the liver enzyme abnormalities must be made, and close monitoring should be initiated in conjunction with the medical monitor and medical safety physician and in accordance with the FDA Guidance for Industry, Drug-Induced Liver Injury: Premarketing Clinical Evaluation, July 2009. The participant should return to the study site and be evaluated as soon as possible, preferably within 48 hours from the time the investigator becomes aware of the abnormal results. This evaluation should include laboratory tests, detailed history, and physical assessment.

### 9.6 Procedures for Unmasking of Study Intervention

The IWRS will be programmed with blind-breaking instructions. In case of an emergency, the investigator has the sole responsibility for determining if unblinding of a participant's study intervention assignment is warranted. Participant safety must always be the first consideration in making such a determination. If the investigator decides that unblinding is warranted, the investigator should make every effort to contact the Allergan Medical Monitor

prior to unblinding a participant's study intervention assignment unless this could delay emergency treatment of the participant. If a participant's study intervention assignment is unblinded, the Allergan Medical Monitor must be notified within 24 hours after breaking the blind. The date and reason that the blind was broken must be recorded in the source documentation.

